5.2 Variables Used for Stratification of Randomization

Not applicable.

6.0 Analysis Conventions

Unless otherwise specified, the efficacy and safety continuous variables will be summarized using the descriptive statistics (including mean, standard deviation, median, minimum and maximum), and for qualitative variables, the number (n) and percentage (%) of subjects with non-missing data per category will be the default summary presentation.

All statistical analyses will be conducted at a two-sided significance level of 0.050 or a one-sided significance level of 0.025 (when rounded to 3 decimal places).

6.1 Definition of Baseline

The baseline visit date is the date when the first dose of study drug is received and

referred to as Day 1. The baseline value for a variable is defined as the last non-missing value on or before the date of the first dose of study drug.

6.2 Definition of Final Observation Value

For subjects who did not discontinue the study before Week 24, final observation is the last non-missing observation collected after the first dose of study drug and on the dose of study drug at Week 24. Final observation for the interim analysis at Week 24 is defined as the last non-missing observation collected after the first dose of study drug and within 70 days after the last dose of study drug for subjects who discontinued the study before Week 24.

Final observation for the final analysis at Week 52 is defined as the last non-missing observation collected after the first dose of study drug and within 70 days after the last dose of study drug.

6.3 Definition of Rx Days (Days Relative to the First Dose of Study Drug)

Rx Days are calculated for each time point of interest and it provides a quantitative measure of days between the event and the first dose date. That is, the Rx Day is calculated as the event date minus the date of first dose of study drug plus 1. The Rx Day will be a negative value when the time point of interest is prior to the date of first dose of study drug, and the Rx Day will be a positive value when the time point of interest is after the first dose date. By this calculation algorithm the first dose day is Rx Day 1, while the day prior to the date of first dose is defined as Rx Day –1 (there is no Rx Day 0). Rx days are used to map actual study visits to the protocol specified study visits.

6.4 Definition of Analysis Windows

Since subjects do not always adhere to the study visit schedule, the following rules will be applied to assign actual visits to protocol-specified visits including early termination visits.

For each study visit mentioned in the protocol, a nominal or target day will be selected to represent the corresponding visit along with a window around the target day. Windows will be selected in a non-overlapping fashion so that a date collected on the CRF does not correspond to multiple visit windows. Moreover, windows will not discard any post baseline measurement recorded on the CRF. If a subject had two or more actual visits in one visit window, the visit closest to the target will be used as the study visit for that window. If two visits are equal distance from the target, then the later visit will be used for reporting.

The protocol specified visits and corresponding time windows used in the analyses are presented in Table 2, Table 3, Table 4 and Table 5.

The following visit windows will be used for the analysis of assessment of each efficacy variables which are collected at baseline visit and Week 52 Visit or early termination (ET).

Table 2.**Visit Windows for Analysis of Efficacy Variables, General Laboratory Parameters (Blood Chemistry and Hematology)**

Scheduled Week	Nominal Day	Time Window (Rx Day Range)
Day 1	1	≤ 1
Week 2	15	2 – 22
Week 4	29	23 – 43
Week 8	57	44 – 71
Week 12	85	72 – 99
Week 16	113	100 – 141
Week 24	169	142 – 211
Week 36	253	212 – 309
Week 52	365	310 – 421

Table 3.**Visit Windows for Analysis of DLQI, SF-36, Laboratory Parameters (Urinalysis)**

Scheduled Week	Nominal Day	Time Window (Rx Day Range)
Day 1	1	≤ 1
Week 8	57	2 – 85
Week 16	113	86 – 141
Week 24	169	142 – 211
Week 36	253	212 – 309
Week 52	365	310 – 421

Table 4. Visit Windows for Analysis of Vital Signs

Scheduled Week	Nominal Day	Time Window (Rx Day Range)
Day 1	1	≤ 1
Week 2	15	2 – 22
Week 4	29	23 – 43
Week 8	57	44 – 71
Week 12	85	72 – 99
Week 16	113	100 – 127
Week 20	141	128 – 155
Week 24	169	156 – 183
Week 28	197	184 – 211
Week 32	225	212 – 239
Week 36	253	240 – 267
Week 40	281	268 – 295
Week 44	309	296 – 323
Week 48	337	324 – 351
Week 52	365	352 – 379

Visit Windows for Dose Escalation Analysis Set

The study days for the analysis of dose escalation effect will be calculated with reference to the dose escalation date.

Study Day = Date of evaluation – date of dose escalation + 1.

Table 5. Visit Windows for GPP skin score relative to dose escalation

Scheduled Week	Nominal Day	Time Window (Rx Day Range)
Day 1 (= date of dose escalation)	1	≤ 1
Week 2	15	2 – 22
Week 4	29	23 – 36
Week 6	43	37 – 50
Week 8	57	51 – 64
Week 10	71	65 – 78
Week 12	85	79 – 92
Week 14	99	93 – 106
Week 16	113	107 – 120
Week 18	127	121 – 134
Week 20	141	135 – 148
Week 22	155	149 – 162
Week 24	169	163 – 176
Week 26	183	177 – 190
Week 28	197	191 – 204
Week 30	211	205 – 218
Week 32	225	219 – 232
Week 34	239	233 – 246
Week 36	253	247 – 260
Week 38	267	261 – 274
Week 40	281	275 – 288
Week 42	295	289 – 302
Week 44	309	303 – 316

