2 weeks of the last dose of study drug, and preferably prior to the initiation of another therapy. However, these procedures should not interfere with the initiation of any new treatments or therapeutic modalities that the Investigator feels are necessary to treat the subject's condition. Following discontinuation of the study drug, the subject will be treated in accordance with the Investigator's best clinical judgment.

A final phone call will be made to the subject approximately 70 days after the last dose of study drug to determine the status of any ongoing AEs/SAEs or the occurrence of any new AEs/SAEs.

All attempts must be made to determine the date of the last dose of study drug and the primary reason for PD. The information will be recorded on the appropriate eCRF page.

For subjects that are considered lost to follow-up, reasonable attempts must be made to obtain information on the final status of the subject. At a minimum, two phone calls must be made and one certified letter must be sent.

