5.5 Treatments

5.5.1 Treatments Administered

Subjects will receive adalimumab 80 mg (2 syringes) at Baseline (Week 0) by subcutaneous injection. At and after Week 2, subjects will receive 40 mg (1 syringe)

every other week (eow) subcutaneously until Week 50. No study drug administration will occur at Week 52.

Dose Escalation

For subjects who meet dose escalation criteria on or after Week 8, 80 mg (2 syringes) doses will be administered subcutaneously every other week until study end. No dose reduction will be allowed after dose escalation throughout the study. The dose escalation criteria are defined as the subjects who do not achieve Clinical Response (i.e., minimal improvement, unchanged or worsened) on or after Week 8 ([Appendix I](#)).

Prior to dose escalation, the observation result of skin lesions (GPP skin score, PGA and PASI score) will be recorded. Blood draw for the laboratory test (including WBC, hs-CRP and serum albumin for systemic/laboratory score) and measurement of pharmacokinetics and AAA will be also performed, prior to dose escalation.

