6.5 Definition of Missing Data Imputation

The following methods will be used to impute missing values in the efficacy analyses. In general, missing Baseline and safety data will not be imputed. In addition, an observed case analysis will be performed.

Baseline Value is Missing

Subjects will be excluded from analysis of change from baseline if baseline evaluation is missing.

Non-Responder Imputation (NRI)

The NRI approach is used for binary efficacy variables. These variables can take values of 'Achieved' or 'Not Achieved' or may be missing for any reason including discontinuation from study. According to the NRI imputation approach, all missing value will be considered as 'Not Achieved.'

Last Observation Carried Forward (LOCF)

For continuous variables, the following rules will be used for the LOCF approach:

1. Baseline and pre-baseline values will not be used to impute the missing post-baseline values.
2. Missing values after Study Day 1 will be imputed using the latest non-missing values after Day 1 and prior to the missing value. If there are no non-missing values after baseline, then the LOCF value will be missing.

Observed Cases (OC)

Observed case analysis will be performed such that missing values will not be imputed.

Imputation of Missing Dates

For baseline, efficacy, and safety parameters, if the day and/or month are missing, the following conventions will be used to impute the missing dates:

- 01 for missing start day
- End of month for missing end day

- January 1st for missing start month
- December 31st for missing end month

In case of missing or partially missing dosing dates, the dates will not be imputed.

In case of missing or partially missing adverse event start and stop dates, the dates will be imputed by comparing to the first dosing date so that the corresponding adverse events will be made treatment-emergent, whenever possible.

Rounding

Rounding will be performed only for presentation of results. No rounding will be performed before or during computations. The ROUND function of SAS will be used to round results for presentation.

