10.3 Secondary Efficacy Analyses

Discrete variables will be summarized by counts and percentages, and continuous variables will be summarized by descriptive statistics on the items below at each visit.

The subjects who have missing data for any reason such as early terminated subjects will be included into analysis using NRI for discrete variables or LOCF for continuous variables.

- Proportion of subjects achieving Clinical Response (expect Week 16, which is the primary endpoint).
- Proportion of subjects achieving remission.
- Change from the Baseline in total GPP score (skin and systemic/laboratory test).
- Change from the Baseline in JDA severity index of GPP.
- Change and Percent change from the Baseline in total skin score.
- Change from the Baseline in total systemic/laboratory test score.
- Change from the Baseline in score of erythema area (overall) and BSA (BSA of GPP).
- Change from the Baseline in score of erythema area with pustule and BSA.
- Change from the Baseline in score of edema area and BSA.
- Change from the Baseline in Body temperature.
- Change from the Baseline in WBC.
- Change from the Baseline in hs-CRP.
- Change from the Baseline in serum Albumin.
- Proportion of subjects achieving "Mild" in JDA severity index of GPP for patients with "Moderate" or "Severe" at the Baseline.
- Proportion of subjects achieving Treatment Success in PGA (reduction of 2 grades).
- Change from the Baseline in PGA grade.
- Proportion of subjects achieving PGA 0/1 for patients with PGA grade at least 2 at Baseline.
- Proportion of subjects achieving PASI 90.

- Proportion of subjects achieving PASI 75.
- Proportion of subjects achieving PASI 50.
- Change and Percent change from the Baseline in PASI score.
- Proportion of subjects achieving DLQI = 0.
- Change from the Baseline in DLQI score.
- Change from the Baseline in SF-36 score.
- Proportion of subjects taking systemic co-medication for GPP (etretinate, MTX, oral steroids, cyclosporine).
- Proportion of subjects taking topical co-medication for GPP (corticosteroid, vitamin D3, tacrolimus).

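### The Week 24, 36 and 52 efficacy windows open so early that a score taken at premature discontinuation can count as an observed response, and non-responder imputation then does not act

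*SAP*

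**What the plan says.** SAP 6.4 sets the rule: "For each study visit mentioned in the protocol, a nominal or target day will be selected to represent the corresponding visit". The same section says that its "rules will be applied to assign actual visits to protocol-specified visits including early termination visits", and that "windows will not discard any post baseline measurement recorded on the CRF". If several visits fall in one window, the one nearest the target is used. The sentence introducing Table 2 says that efficacy variables are collected at early termination.

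Table 2 covers efficacy variables and general laboratory tests. It has rows for Weeks 2, 4, 8, 12, 16, 24, 36 and 52, and none for Weeks 20, 28, 32, 40, 44 and 48. Table 4 covers vital signs and has rows for all of these weeks.

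Under SAP 6.5 a binary efficacy variable "may be missing for any reason including discontinuation from study", and a missing value is scored as not achieved. SAP 10.3 adds: "The subjects who have missing data for any reason such as early terminated subjects will be included into analysis using NRI for discrete variables". SAP 6.5 also plans an observed-case analysis.

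Protocol 5.4.1 asks for the discontinuation procedures within "2 weeks of the last dose of study drug, and preferably prior to the initiation of another therapy". After the initial dose, dosing under Protocol 5.5.1 runs "every other week (eow) subcutaneously until Week 50". Footnote a of the study activities table allows 7 days either side of a scheduled visit.

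**The concern.** NRI is meant to be the conservative treatment of subjects who stop early, but it acts only when a window is empty. Where a window opens weeks before its target, the score taken as a subject leaves the study fills it. A subject who was responding on leaving is then reported as a responder at a visit never reached.

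Week 24 is the interim analysis (SAP 4.4). Clinical Response at Weeks 24 and 52 is a secondary endpoint and a subgroup time point (SAP 10.5). With ten subjects, one such case visibly changes the rate.

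A second inconsistency concerns body temperature. Protocol 5.3.1.1 has it measured at every visit, and SAP 10.3 lists its change from baseline as a secondary efficacy variable to be summarised by visit. As an efficacy variable it falls under Table 2, with no row for six visits; as a vital sign it falls under Table 4, which has all of them.

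**Working it through.** **1. Reproducing the windows.** Target day = 1 + 7 × week. Each boundary is the midpoint of neighbouring target days. With Table 2's visits only:

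- Week 24 opens after (113 + 169)/2 = 141, so on Day 142.
- Week 36 opens after (169 + 253)/2 = 211, so on Day 212.
- Week 52 opens after (253 + 365)/2 = 309, so on Day 310.

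With Weeks 20, 32 and 48 (Days 141, 225 and 337) as the preceding neighbours, the midpoints are 155, 239 and 351. The windows then open on Days 156, 240 and 352, as in Table 4. Both tables are reproduced exactly.

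**2. Early reach.**

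| Visit | Target | Table 2 | Table 4 | Days before target, Table 2 / Table 4 | Extra early days |
|---|---|---|---|---|---|
| Week 16 | 113 | 100–141 | 100–127 | 13 / 13 | 0 |
| Week 24 | 169 | 142–211 | 156–183 | 27 / 13 | 14 |
| Week 36 | 253 | 212–309 | 240–267 | 41 / 13 | 28 |
| Week 52 | 365 | 310–421 | 352–379 | 55 / 13 | 42 |

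The protocol's own visit windows open on Days 162, 246 and 358 (target minus 7). Table 2 opens 20, 34 and 48 days before that.

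**3. Which discontinuations are affected.** Assume dosing on schedule (dose day = 7w + 1 for w = 0, 2, …, 50, so 26 possible last-dose weeks) and a discontinuation visit 1 to 14 days after the last dose. Drug is given after the day's assessments, so the dose due at the visit itself is not counted.

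| Last dose | Discontinuation visit | Counted by Table 2 at | Earlier planned doses not given | Days before target |
|---|---|---|---|---|
| Week 20 | Days 142–155 | Week 24 | 1 (Week 22) | 14–27 |
| Week 30 | Days 212–225 | Week 36 | 2 (Weeks 32, 34) | 28–41 |
| Week 32 | Days 226–239 | Week 36 | 1 (Week 34) | 14–27 |
| Week 44 | Days 310–323 | Week 52 | 3 (Weeks 46, 48, 50) | 42–55 |
| Week 46 | Days 324–337 | Week 52 | 2 (Weeks 48, 50) | 28–41 |
| Week 48 | Days 338–351 | Week 52 | 1 (Week 50) | 14–27 |

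This is 6 of 26 last-dose weeks under Table 2. Under Table 4's lower limits it is 0 of 26.

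**4. Effect on the rate.** With n = 10, one reclassified responder is 1/10 = 10 percentage points. For example, 5/10 = 50% (exact 95% CI 18.7–81.3%) becomes 6/10 = 60% (26.2–87.8%).

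**5. Body temperature.** A Week 28 reading on Day 197 belongs to Week 24 under Table 2 (142–211) and to Week 28 under Table 4 (184–211). If the Week 24 visit took place on time, Table 2 does not use the Week 28 reading at all.

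**The case against.** The strongest reply is that Table 2 may be right for its variables. The SAP appears to fit each window table to a collection schedule. Table 3 keeps only the DLQI weeks given in Protocol 5.3.1.1, and its Week 24, 36 and 52 limits are the same as Table 2's. Footnote s of the study activities table foresees visits at which skin scoring and laboratory sampling are not planned. This stands.

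A reader might infer that leaving out six weeks is an error for skin score, PGA, PASI and laboratory tests. The documents do not show it. The activity table cannot be read reliably in the extracted text, and the protocol's instruction to analyse secondary variables at each scheduled visit cannot mean every study visit, because DLQI is on that list. Table 2's weeks equal the pharmacokinetic sampling weeks, which suggests a copying slip but does not prove one.

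A reader might also infer that the windows contradict NRI. They do not. NRI covers missing values, no sentence makes every discontinued subject a non-responder, and SAP 6.4 windows early-termination scores openly. The difficulty is what these rules produce when followed as written.

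The 0-of-26 figure depends on exact dosing. Protocol 5.3.1.1 allows 7 days either side of a dose. A Week 20 dose on Day 148 allows a discontinuation visit up to Day 162, inside Table 4's Week 24 window with the Week 22 dose not given. Table 4's limits alone therefore do not close the gap.

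Finally, SAP 10.1 is descriptive, with no significance level, and an observed-case analysis is planned. That lowers the stakes, but the reported NRI rates are still affected.

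**Conclusion.** The point holds in a limited form. As written, a responding discontinuation score on Days 142–155, 212–239 or 310–351 is an observed response at Week 24, 36 or 52. Compared with Table 4's lower limits, this can only leave the NRI rate unchanged or raise it, by 10 points per responder at n = 10. In the observed-case analysis the effect can go either way. Earlier discontinuations leave the window empty and NRI acts. A discontinuation score that follows an on-time target visit is not used, because the nearer visit is chosen.

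That planned doses were missed in these cases rests on on-schedule dosing and a discontinuation visit within 14 days of the last dose. The documents give no discontinuation rate, so the number affected is unknown and may be zero.

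A reader might extend this to the primary endpoint. The documents do not support that: Week 16 opens on Day 100 in both tables. Only its late limit differs (Day 141 against Day 127), which matters only for a subject with no score on Days 100–127 and a score on Days 128–141.

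By-visit coverage is shown to be inconsistent for body temperature alone. This is worth correcting because it is cheap; it does not threaten the main result.

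**What to change.** 1. Add to SAP 6.4 and 6.5: for binary efficacy endpoints, a premature-discontinuation score taken before the protocol visit window (before Day 162, 246 or 358 for Weeks 24, 36 or 52) is not observed at that visit, and NRI applies. The score stays in listings, in LOCF and at its own earlier time point.
2. Start the Week 24, 36 and 52 efficacy windows on Days 156, 240 and 352. Add rows for Weeks 20, 28, 32, 40, 44 and 48 only for variables planned at those visits, at least body temperature. Adding them for every variable could produce false response rates near 0% where nothing was due.
3. Qualify the no-discard sentence to match. For a variable without the extra rows, Days 142–155, 212–239 and 310–351 would fall in no by-visit window.

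No new data are needed. The cost is that a subject whose only score is an early discontinuation score becomes a non-responder, so the reported rate may be slightly lower. This includes a subject seen on Days 156–161, 240–245 or 352–357 who had missed no dose before that visit.

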6.5 Definition of Missing Data Imputation

The following methods will be used to impute missing values in the efficacy analyses. In general, missing Baseline and safety data will not be imputed. In addition, an observed case analysis will be performed.

Baseline Value is Missing

Subjects will be excluded from analysis of change from baseline if baseline evaluation is missing.

Non-Responder Imputation (NRI)

The NRI approach is used for binary efficacy variables. These variables can take values of 'Achieved' or 'Not Achieved' or may be missing for any reason including discontinuation from study. According to the NRI imputation approach, all missing value will be considered as 'Not Achieved.'

Last Observation Carried Forward (LOCF)

For continuous variables, the following rules will be used for the LOCF approach:

1. Baseline and pre-baseline values will not be used to impute the missing post-baseline values.
2. Missing values after Study Day 1 will be imputed using the latest non-missing values after Day 1 and prior to the missing value. If there are no non-missing values after baseline, then the LOCF value will be missing.

Observed Cases (OC)

Observed case analysis will be performed such that missing values will not be imputed.

Imputation of Missing Dates

For baseline, efficacy, and safety parameters, if the day and/or month are missing, the following conventions will be used to impute the missing dates:

- 01 for missing start day
- End of month for missing end day

- January 1st for missing start month
- December 31st for missing end month

In case of missing or partially missing dosing dates, the dates will not be imputed.

In case of missing or partially missing adverse event start and stop dates, the dates will be imputed by comparing to the first dosing date so that the corresponding adverse events will be made treatment-emergent, whenever possible.

Rounding

Rounding will be performed only for presentation of results. No rounding will be performed before or during computations. The ROUND function of SAS will be used to round results for presentation.

The mean and median will be rounded for presentation to one decimal more than the data were entered into the database. For example, mean systolic blood pressure will be presented to one decimal place (125.2 mmHg) when it is recorded to integer level in the database (110 mmHg). The standard deviation will be rounded to two decimal places more than the data were entered into the database (e.g., 25.31 mmHg for systolic blood pressure). The minimum and maximum values will be presented as entered into the database.

Percentages will be rounded for presentation to one decimal place; e.g., the proportion 0.1244 will be reported in percent as 12.4.

7.0 Demographics, Baseline Characteristics, Medical History, and Previous/Concomitant Medications

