5.3 Efficacy, Pharmacokinetic, and Safety Assessments/Variables

5.3.1 Efficacy and Safety Measurements Assessed and Flow Chart

Study procedures will be performed as summarized in Section 5.3.1.1. All subjects must meet the study selection criteria outlined in Section 5.2.1 and Section 5.2.2 in order to be enrolled into the study.

Table 1. Study Activities

Activity	Screening (Day -30 to Day -1)	Baseline ^a (Day 1)	Wk 2	Wk 4	Wk 8	Wk 12	Wk 16	Wk 20	Wk 24	Wk 28	Wk 32	Wk 36	Wk 40	Wk 44	Wk 48	Wk 52 or Premature Discontinuation Visit	Unscheduled Study Visit	70- Day Call
Informed Consent	X																	
Assign Subject ID Number	X																	
Subject Background	X																	
Inclusion/Exclusion Criteria	X	X ^b																
Medical/Surgical History	X	X ^b																
Prior and Concomitant Therapy Assessment	X	X ^b	X	X	X	X	X	X	X	X	X	X	X	X	X	X	X	
Alcohol Use	X																	
Tobacco Use	X																	
Physical Exam ^c	X	X	X	X	X	X	X	X	X	X	X	X	X	X	X	X	X	
Chest X-Ray/12-Lead ECG ^e	X															X ^f	X ^g	
TB Screening ^h	X																	
Vital Signs	X ⁱ	X	X	X	X	X	X	X	X	X	X	X	X	X	X	X	X	
Pregnancy Tests	X ^j	X ^k														X ^k		
General Labs ^l : Blood Chemistry and Hematology	X	X ^m	X	X	X	X	X	X	X	X	X	X	X	X	X	X ^s	X	

Table 1. Study Activities (Continued)

Activity	Screening (Day -30 to Day -1)	Baseline ^a (Day 1)	Wk 2	Wk 4	Wk 8	Wk 12	Wk 16	Wk 20	Wk 24	Wk 28	Wk 32	Wk 36	Wk 40	Wk 44	Wk 48	Wk 52 or Premature Discontinuation	Unscheduled Study Visit	70- Day Call
Urinalysis ⁿ	X	X														X		
HIV Screen ^o	X																	
Hepatitis B Screen ^p	X																	
Hepatitis C Screen	X																	
Antinuclear Antibody (ANA)/Anti-Double- Stranded DNA (dsDNA) ^q																		
Photography ^r	X	X	X	X	X	X	X	X	X	X	X	X	X	X	X	X		
GPP Skin Score and BSA, Systemic/Laboratory Score	X	X	X	X	X	X	X	X	X	X	X	X	X	X	X	X ^s		
PGA	X	X	X	X	X	X	X	X	X	X	X	X	X	X	X	X	X ^s	
PASI Score	X	X	X	X	X	X	X	X	X	X	X	X	X	X	X	X	X ^s	
DLQI		X														X		
SF-36		X														X		
Dispense Study Drug	X	X	X	X	X	X	X	X	X	X	X	X	X	X	X	X	X ^s	
Administer Study Drug ^t	X	X	X	X	X	X	X	X	X	X	X	X	X	X	X	X	X ^s	
PK Measurements ^u	X	X	X	X	X	X	X	X	X	X	X	X	X	X	X	X	X ^s	
AAA Measurements ^u	X	X	X	X	X	X	X	X	X	X	X	X	X	X	X	X	X ^s	

Table 1. Study Activities (Continued)

Activity	Screening (Day -30 to Day -1)	Baseline ^a (Day 1)	Wk 2	Wk 4	Wk 8	Wk 12	Wk 16	Wk 20	Wk 24	Wk 28	Wk 32	Wk 36	Wk 40	Wk 44	Wk 48	Wk 52 or Premature Discontinuation Visit	Unscheduled Study Visit	70- Day Call

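### Scores taken at a premature-discontinuation visit after a replacement GPP therapy has started are analysed as ordinary adalimumab data

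*SAP*

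**What the plan says.** **Timing of the PD visit.** Protocol 5.4.1 asks for the PD procedures within "2 weeks of the last dose of study drug, and preferably prior to the initiation of another therapy". It adds that "these procedures should not interfere with the initiation of any new treatments or therapeutic modalities that the Investigator feels are necessary". In Protocol Table 1 the skin score, PGA and PASI belong to the shared column "Wk 52 or Premature Discontinuation Visit".

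**Windowing.** SAP 6.4 states that "the following rules will be applied to assign actual visits to protocol-specified visits including early termination visits", and that "windows will not discard any post baseline measurement recorded on the CRF". Where two visits share a window, the one nearer the target day is used, and the later one if they tie.

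**Missing data.** SAP 6.5 applies NRI to binary efficacy variables whose value is missing. For continuous variables the LOCF rule is: "Missing values after Study Day 1 will be imputed using the latest non-missing values after Day 1 and prior to the missing value". The only values it bars from being carried forward are those from Baseline or before. SAP 10.2 uses NRI for the primary endpoint. SAP 10.3 keeps subjects who terminate early in the secondary analyses through NRI or LOCF.

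Neither document says what to do with an efficacy score taken after a new GPP therapy has begun.

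**The concern.** The permission in Protocol 5.4.1 is a matter of patient care and is not questioned here. Its consequence is that some PD scores may reflect another drug, and the analysis plan must say how they are used. As written, such a score reaches the results by two routes. It can be the selected value at an analysis visit, where it also counts in binary endpoints because NRI fills only gaps. It can also be carried to later visits for continuous secondary variables.

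This is a single-arm, open-label study of 10 subjects. No comparator would share the misattribution, and each subject is a tenth of every result.

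**Working it through.** The plan gives no figure for this point, so the check traces the rules and then counts how often they let a PD score through.

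**Inputs**
- Last dose at Week w = 0, 2, ..., 48, on day 7w + 1 (Protocol 5.5.1): 25 possibilities. Week 50 is left out because the PD visit and Week 52 then coincide (days 352–365).
- PD visit 1 to 14 days after the last dose (Protocol 5.4.1): 14 possibilities. In all, 25 × 14 = 350 timings.
- Scheduled visits on their nominal days up to the last dose (Protocol 5.1).
- Windows and targets from SAP Table 2. DLQI and SF-36 (Table 3) and vital signs (Table 4) have their own windows and are not counted here.

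**Selection rule.** The PD score is the window's value if |PD day − target| ≤ |other visit day − target| for every other visit in that window. Ties go to the PD visit because it is later.

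**Result**
- Selected on all 14 days after a last dose at Weeks 0, 6, 10, 14, 20, 22, 30, 32, 34, 44, 46 and 48: 12 × 14 = 168.
- Selected on 7 of 14 days after Week 2.
- Never selected after Weeks 4, 8, 12, 16, 18, 24, 26, 28, 36, 38, 40 and 42, because an on-drug visit is nearer the target.
- Total 168 + 7 = 175 of 350, or 50%.

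**Two cases that matter most**
- *Last dose at Week 14 (day 99).* The PD visit falls on days 100–113. The Week 16 window is days 100–141 and holds no other visit. The PD score is the Week 16 value, it is not missing, and NRI does not apply.
- *Last dose at Weeks 44, 46 or 48 (days 309, 323, 337).* The PD visit falls on days 310–351, inside the Week 52 window (310–421, target 365). Even after Week 48 it wins: the Week 48 visit is 365 − 337 = 28 days from target, the PD visit 27 to 14 days. It becomes the Week 52 value with no imputation.

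**Raw or windowed LOCF.** The SAP does not say which values LOCF works on. On windowed values, the 175 of 350 count applies. On raw values, the PD score is the latest observation at every timing and all 350 are exposed.

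**Size (assumed, since no dropout or rescue rate is given)**
- Continuous: shift in the mean = d/10 for a replacement effect of d points in one subject. For d = 1 to 3 on the skin score, the shift is 0.1 to 0.3. For PASI percent change, individual effects of 25, 50 or 75 points shift the mean by 2.5, 5.0 or 7.5 points.
- Primary: the exact (Clopper–Pearson) limits are the 2.5% quantile of Beta(x, 11 − x) and the 97.5% quantile of Beta(x + 1, 10 − x). For x = 3 they are 6.7% and 65.2%. For x = 4 they are 12.2% and 73.8%.
- The step from 3 to 4 is the one that the sample-size argument in SAP 4.3 turns on. Under a 10% response rate, P(X ≥ 3) = 0.0702 and P(X ≥ 4) = 0.0128. Under 50%, P(X ≥ 4) = 0.828, which agrees with the stated exact power of 82%.

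**The case against.** - **The exposure is limited.** The PD visit is preferred before new therapy and due within two weeks of the last dose, so time on the new agent is short if the schedule is kept. This stands: the problem is possible, not certain.
- **The primary uses NRI, efficacy is descriptive, and an observed-case analysis is planned.** SAP 10.1 defines no significance level, and the observed-case results will show what carry-forward adds. But neither NRI nor the observed-case analysis removes a PD score that sits in its own window, because that score is an observed value.
- **Removing the score can itself favour the drug.** Take a subject who responded at the last on-drug visit, flared, started another agent and was scored the next day. That PD score records the failure, and deleting it carries the earlier response forward. With assumed changes of −3 on drug and +2 at PD, the mean moves by (−3 − 2)/10 = −0.5, towards adalimumab. This stands and shapes the fix.

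A reader might infer more than the documents support:
- *That the bias always favours adalimumab.* It does not; a PD score soon after a flare may be worse than the last on-drug score.
- *That the PD score is always carried to Week 52.* That holds only if LOCF works on raw values.
- *That means shift by 0.5 to 1.0 skin-score points.* That needs a 5-point swing in one or two subjects, for which the documents give no basis.
- *That SAP 6.2 lets in efficacy scores long after treatment.* The final observation defined there may date from up to 70 days off drug, but SAP 10.3 analyses efficacy at each visit, and final values appear only in the laboratory analyses (SAP 11.3). The 70-day contact concerns adverse events, and Table 1 schedules no skin score after the Week 52/PD visit.

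**Conclusion.** The gap is real and worth closing as a cheap improvement. Following the plan as written can credit adalimumab with a replacement drug's effect, at the primary time point as well as in secondary variables. On nominal visit days half of the PD timings are exposed through windowing, and all of them if LOCF uses raw values.

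The consequence depends on how many subjects switch therapy before the PD visit, which the documents do not allow one to estimate. If one does, a mean moves by 0.1 per point of replacement effect. One added Week 16 responder (3/10 to 4/10) would lift the lower exact limit from below to above the 10% threshold rate used for sample size, although no formal test is defined. The direction of the error cannot be stated in advance.

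**What to change.** Add to SAP 6.4 and 6.5:

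- Efficacy assessments dated after the start of a new systemic, biologic, phototherapy or apheresis treatment for GPP, begun after the last dose of study drug, are set to missing before windowing. A score on the start date is kept if it was taken before the new therapy was given.
- Binary variables, including the primary endpoint, are then Not Achieved by NRI at the analysis visit that the removed score would have supplied.
- For continuous variables, LOCF uses the last windowed value before the new therapy. This also settles the raw-or-windowed question.
- The as-observed result, with the PD score included, is shown as a sensitivity analysis, because the cut can also drop a score that records failure.

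SAP 6.2 needs no change on this account.

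**Cost.** SAP wording, one date comparison in programming and one added sensitivity table. Protocol 5.2.3.2 already has changes in concomitant medication recorded on the eCRF through the Week 52/PD visit; the order of events on a shared date may need a site query. A few observed PD scores leave the main efficacy tables. Safety analyses and clinical procedures are unaffected.
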